4.2.3 Analysis of the primary efficacy variable

The primary variable is the time to first event included in the primary composite endpoint. The primary analysis will be based on the ITT principle using the FAS, including events with onset on or prior to PACD, adjudicated and confirmed by the CEA committee.

In the analysis of the primary composite endpoint, treatments (dapagliflozin versus placebo) will be compared using a Cox proportional hazards model with a factor for treatment group, stratified by T2D status at randomization, and adjusting for history of hospitalization for heart failure. The analysis will use WoC, non-CV death, last clinical event assessment and PACD for censoring of patients without any primary event as described in Section 3.1. The Efron method for ties and p-value based on the score statistic will be used. The event rates, p-value, HR, and 95% confidence interval will be reported.

The contribution of each component of the primary composite endpoint to the overall treatment effect will be examined. In the analysis of the components, all first event of the given type will be included irrespective of any preceding non-fatal composite event of a different type. Consequently, the sum of the number of patients with events in the component analysis will be larger than the number of patients with composite events. Methods similar to those described for the primary analysis will be used to separately analyze the time from randomization to the first occurrence of each component of the primary composite endpoint.

Kaplan-Meier estimates of the cumulative proportion of patients with event will be calculated and plotted, for the composite endpoint and for the individual components.

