4.2.4.1 Analysis of recurrent HF events and CV death

The composite outcome of recurrent HF hospitalizations or CV death will be analysed by the semi-parametric proportional rates model (Lin et al 2000) known as the LWYY (Lin-Wei-Yang-Ying) method, to test the treatment effect and to quantify the treatment difference in

terms of the rate ratio with 95% confidence interval and p-value. Recurrent HF hospitalizations, CV death and censoring processes all have continuous distributions so that HF hospitalization and death cannot happen at the same time. If a HF hospitalization and CV death occurred at the same day, then only CV death will be counted. Moreover, CV death is a terminating event which, unlike censoring, prevents the occurrence of new HF hospitalizations.

In addition, the two components in the composite endpoint (total HF hospitalizations and CV death) will be analysed separately to quantify the respective treatment effects and check the consistency between the composite and the components. For the analysis of total HF hospitalizations component, occurrence of CV death can be regarded as semi-competing risk (informative censoring) and may introduce a bias in the treatment effect estimate for HF hospitalizations (dilution of effect size if the drug has a positive effect on both components). In order to address this concern and to account for the correlation between the two components, the joint modelling (frailty model) approach (Rogers et al 2016) will be used for the component analyses.

For joint frailty analysis the following assumptions are made: (Liu et al 2004)

- As noted above, HF hospitalization and death cannot happen at the same day (only the CV death will be counted) and CV death is a terminating event which prevents the occurrence of new HF hospitalizations.
- The hazard function of CV death (the instantaneous risk of death given that the subject is still alive) follows a proportional hazards model with constant baseline hazard, stratified by T2D status at randomization with treatment and history of hospitalization for heart failure as covariates.
- The hazard function of recurrent HF hospitalizations (the instantaneous risk of having another HF hospitalization given that the subject is still alive) follows a proportional hazards model as well, with constant baseline hazard, stratified by T2D status at randomization with treatment and history of hospitalization for heart failure as covariates.

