- Within subject recurrent HF hospitalizations and CV death are correlated events. This correlation varies from subject to subject. To account for this correlation, the hazard function of recurrent HF hospitalizations and hazard function of CV death are modeled by a joint a subject specific random frailty term which follows a gamma distribution with unit mean and unknown variance.
- Censoring (including non-CV death) is noninformative, in particular it does not depend on random frailty.

Estimation in the frailty proportional hazards model will be done using Gaussian quadrature approach (Liu and Huang 2008, Lu and Liu 2014, SAS Institute Inc. 2018). Since SAS PROC NLMIXED supports only normal distributions, a probability integral transformation to generate numbers from a gamma distribution will be used (Nelson et al 2006) following Liu and Huang 2008.

Additionally, non-parametric estimates of the marginal mean of the cumulative number of recurrent HF hospitalization rates over time will be calculated allowing for death as terminal event, and the estimates will be plotted (Ghosh and Lin 2000). The estimation will be done in SAS using the PROC PHREG and by treating the situation as competing risks with several records per subject (Andersen et al 2019)

4.2.4.2 Analysis of change from baseline at 8 months in the KCCQ total symptom score

Hypothesis testing

The composite rank-based endpoint representing the patients' vital status at 8 months and the change from baseline to 8 months in TSS in surviving patients, as defined in Section 3.2.3, will be analysed using the rank ANCOVA method (Stokes et al 2012) to test the null hypothesis of no differences in the distributions of ranked outcomes between the two treatment groups. Analysis will be stratified by T2D status at randomisation, and adjusted for the baseline TSS value as follows.

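### The joint frailty model in SAP 4.2.4.1 has no association parameter, so one variance must describe both the clustering of HF hospitalizations and their link to CV death

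*SAP*

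**What the plan says.** SAP 4.2.4.1 tests the second secondary endpoint with the LWYY proportional rates model, which contains no frailty. The two components then "will be analysed separately to quantify the respective treatment effects and check the consistency between the composite and the components". Because CV death may act as informative censoring for hospitalizations, the section continues: "In order to address this concern and to account for the correlation between the two components, the joint modelling (frailty model) approach" will be used for the components.

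A list of assumptions follows. Each hazard "follows a proportional hazards model with constant baseline hazard, stratified by T2D status at randomization", with treatment and prior HF hospitalization as covariates. On dependence the SAP says: "Within subject recurrent HF hospitalizations and CV death are correlated events. This correlation varies from subject to subject". To capture this, both hazards are "modeled by a joint a subject specific random frailty term which follows a gamma distribution with unit mean and unknown variance". The variance is the only unknown named for the frailty; there is no exponent, loading or second variance. Estimation is by Gaussian quadrature in PROC NLMIXED.

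Elsewhere, SAP 4.2.3 plans to "separately analyze the time from randomization to the first occurrence of each component of the primary composite endpoint", which gives CV death its own Cox-type analysis. A non-parametric marginal mean curve for hospitalizations, allowing for death, is also planned, but as a plot.

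**The concern.** A programmer following this text multiplies both hazards by the same v. A patient with twice the average hospitalization hazard then has exactly twice the average CV-death hazard. The frailty variance has two jobs: to describe how clustered hospitalizations are within patients, and how strongly they go with CV death. Strong clustering with a weak link to death cannot be represented. Zero variance removes both features, and any positive variance imposes both. Relaxing the constant baseline hazards would not change this.

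The model was chosen to handle this dependence, and its results are meant to quantify the component effects and check them against the composite. If the restriction is wrong, the standard errors are affected first. For total HF hospitalizations the SAP plans no other treatment-effect estimate against which to notice it.

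**Working it through.** **Plan's own figure.** The SAP gives none for the joint model. As a check on the general inputs in SAP 1.4 (HR 0.80, one-sided 2.5%, 90% power, 1:1), events = 4 × (1.960 + 1.282)² / (ln 0.80)² = 4 × 10.507 / 0.04979 ≈ 844, as stated.

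**Algebra.** Let v be gamma with mean 1 and variance θ. For a patient with n hospitalizations, death indicator d (0 or 1) and total cumulative hazard Λ for both processes, integrating v out of the model as written gives a frailty contribution of

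θ^(n+d) × Γ(1/θ + n + d) / Γ(1/θ) × (1 + θΛ)^−(1/θ + n + d).

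The counts enter only as n + d, so for the frailty a CV death is one more hospitalization. At equal Λ, the implied CV-death risk after n hospitalizations relative to none is 1 + nθ. With a free exponent, v^(n+d) becomes v^(n+αd) and the CV-death cumulative hazard is multiplied by v^α. This needs quadrature, which is already planned.

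**Simulation inputs.** From SAP 1.4: 4500 patients, 1:1, average follow-up 24 months (simulated as uniform over 15–33 months). Assumed: placebo rates of 0.14 HF hospitalizations and 0.08 CV deaths per year (ranges 0.10–0.18 and 0.06–0.10), HRs 0.75 and 0.80, θ of 2 or 5, and CV-death hazard proportional to v^a. T2D strata and prior HF hospitalization were left out. There were 300 trials per main cell, 150 for range checks and 15 for free-exponent fits.

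**Model as written** (300 trials per cell):

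| True θ | True a | Fitted θ | HF HR (true 0.75) | CV-death HR (true 0.80) |
|---|---|---|---|---|
| 2 | 0 | 1.09 | 0.739 | 0.790 |
| 5 | 0 | 2.35 | 0.736 | 0.777 |
| 2 | 0.5 | 1.60 | 0.750 | 0.800 |
| 5 | 0.5 | 3.88 | 0.743 | 0.778 |
| 2 | 1 | 1.99 | 0.745 | 0.796 |
| 5 | 1 | 4.97 | 0.748 | 0.789 |

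With a log-HR SE near 0.10, Monte Carlo error is about 0.10/√300 = 0.006, so the HR shifts are known only to within about 1%.

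**Standard errors of the log HR, as written against the comparator.** The comparator is separate models at a = 0 and the free-exponent fit in the same data at a = 0.5.

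| θ | a | CV death | HF hospitalization |
|---|---|---|---|
| 2 | 0 | 0.088 v 0.082 (+8%) | 0.071 v 0.077 (−7%) |
| 5 | 0 | 0.096 v 0.082 (+16%) | 0.080 v 0.093 (−14%) |
| 2 | 0.5 | 0.092 v 0.086 (+7%) | 0.076 v 0.079 (−4%) |
| 5 | 0.5 | 0.108 v 0.096 (+12%) | 0.093 v 0.098 (−5%) |

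Percentages at a = 0 use unrounded values. At θ = 5, a = 0, the assumed rate range gives +13% to +19% for CV death and −12% to −17% for HF (0.089 v 0.101; 0.074 v 0.089).

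The two errors differ in kind. At a = 0 the CV-death SE roughly matches the empirical spread (0.088 v 0.087; 0.096 v 0.100), so precision is lost. The HF SE understates the spread (0.071 v 0.077; 0.080 v 0.093), and the 95% interval covers 93% and 91%.

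**Intermediate case** (rates 0.13 and 0.07, θ = 4, a = 0.3). Fitted θ is about 2.75. The CV-death SE is 0.103 v 0.092 with a free exponent (+12%). The HF SE is 0.086 v 0.095 (−9%), with HF coverage 92%. In a fit to 1.5 million patients the HRs are 0.745 and 0.783.

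**Spurious association.** At a = 0 the true relative CV-death risk after two hospitalizations is 1. The model as written implies 1 + 2 × 1.09 = 3.2 and 1 + 2 × 2.35 = 5.7.

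**Stronger link, a = 1.5.** The CV-death HR is 0.817 at θ = 2 and 0.797 at θ = 1 (150 trials each), so the shift is towards 1 or absent.

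**Null CV-death effect, a = 0.** HRs are 0.749–0.757 and 1.001–1.004, essentially unshifted; the CV-death SE is still 8–17% larger.

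**Freeing the exponent.** At a = 0 it recovers θ (1.99 and 4.95), an exponent near 0 and a CV-death SE of 0.082. Likelihood-ratio statistics against an exponent of 1 average 18.0 (θ = 2, a = 0.5) and 32.9 (θ = 5, a = 0.5), against a 5% critical value of 3.84. At a = 1 the extra parameter moves the CV-death SE only from 0.1166 to 0.1171.

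**The case against.** The SAP never says the frailty acts with equal strength. It refers to published work for the approach and the program, and those sources are not at hand; the intended code may scale the frailty. That stands as a reason to word the point as what the text specifies. It does not remove the point, because the section lists the model's assumptions and names only one unknown for the frailty.

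Nothing in the SAP shows that the link is weaker than proportional, and the case a = 0 contradicts its premise that the events are correlated. This also stands: every effect is conditional on a. But a = 0.3 and 0.5 are correlated cases and show the same errors, mostly smaller.

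The scenarios are not calibrated to the trial. The variances are assumed, the event rates were not fitted to the SAP's 11% annual placebo rate for the primary composite, and the omitted covariates would absorb some heterogeneity. The sizes are therefore indicative.

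A reader might infer that both HRs are materially biased away from 1. The figures do not support this: shifts of 0–3% are small beside SEs of 0.07–0.11, and the CV-death shift reverses at a = 1.5. A reader might also infer that the second secondary endpoint's test, or the trial's CV-death result, is compromised. The LWYY test has no frailty, and SAP 4.2.3 analyses CV death separately. SAP 4.1 treats confidence intervals as descriptive.

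**Conclusion.** The point holds in a limited form. As written, the joint model cannot separate HF over-dispersion from the HF–death link. If the link is weaker than proportional, then under the assumed rates and variances of 2 to 5 the fitted variance is too low. The CV-death SE is about 7–19% larger than needed. The HF-hospitalization SE is about 5–14% too small at central rates (4% in the mildest cell, up to 17% over the rate range at variance 5 with no link). HR shifts are at most about 1–3%. If the link is exactly proportional, nothing is wrong.

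The narrow HF-hospitalization interval matters most, because no other planned analysis estimates the treatment effect on total HF hospitalizations as a component. It would be too strong to say that the model fails to account for the correlation: it does so under an untested one-parameter restriction. The confirmatory conclusions are not at risk. This is a cheap improvement to a supportive analysis.

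**What to change.** In SAP 4.2.4.1, state that the frailty enters the HF-hospitalization hazard as v and the CV-death hazard as v to the power alpha. Estimate alpha in the same NLMIXED program and report it with its 95% CI beside the frailty variance. Pre-specify the alpha = 1 fit as the fallback if the model does not converge. At minimum, keep the present model, state explicitly that alpha is fixed at 1, and add the free-alpha fit as a sensitivity analysis.

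The cost is a sentence or two in the SAP, one extra parameter and some risk of slow convergence. If the present assumption is right, almost no precision is lost.

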First the change from baseline to 8 months in TSS and vital status at 8 months, as well as values of the baseline TSS covariate will be transformed to standardized ranks, using fractional ranks and mean method for ties. Ranking for the composite endpoint will be done so that patients who died prior to the 8-month assessment are assigned the worst ranks within each stratum. Among the deceased the relative ranking will be based on their last value of change from baseline in TSS while alive before deriving fractional ranks. Then, separate regression models will be fit to the ranked data for each randomization stratum using a regression model for the ranked composite variable as dependent variable, adjusting for the ranked baseline covariate. Residuals from this regression model will be captured for further testing of differences between treatment groups. The Cochran-Mantel-Haenszel (CMH) test, stratified for the T2D status at randomization, using the values of the residuals as scores will be used to compare treatment groups.

Responses missing for reasons other than death will be imputed as described in section 'Handling of missing data'.

The p-value from the CMH test of treatment effect at 8 months will be used for the confirmatory statistical testing of the 3rd secondary endpoint in the multiple testing procedure described in section 4.1.3

Estimation of treatment effect

Win ratio:

For a summary statistic that uses the same ranking as that used in the hypothesis test, but has a clinical interpretation, the win ratio (WR) and the corresponding 95% confidence interval (Wang and Pocock 2016) will be reported. It is noted that the WR differs from the statistic used for hypothesis testing, so that exact consistency is not expected between these two analyses, e.g. on rare occasions, the confidence interval for WR could exclude unity while the pre-planned hypothesis test could be non-significant, or the hypothesis test could be

significant with the confidence interval for WR including unity. Formal inference for the superiority of the treatment over control will be made only from the preplanned hypothesis test.

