The win ratio represents the odds of having a more favourable outcome versus a less favourable outcome when assigned to the dapagliflozin 10 mg treatment group as opposed to placebo. More specifically, each patient in the dapagliflozin group is compared with each patient in the placebo group and each pair is labelled as “winner”, “loser”, or “tie”, depending on whether the patient on dapagliflozin has a more favourable, less favourable, or the same outcome, respectively, with respect to the composite ranked endpoint compared to the patient on placebo. Win ratio is defined as the ratio of the number of “winner” pairs to the number of “loser” pairs for the dapagliflozin arm. If the estimated win ratio is greater than 1 then the treatment effect is estimated to be in favour of dapagliflozin.

The win ratio statistic adjusted for the randomization stratification factor and baseline TSS will be obtained using the methodology in

Koch et al 1998, Kawaguchi et al 2011 for the stratified Mann-Whitney estimators for the comparison of two treatments with randomization-based covariance adjustment. The win ratio statistic will be calculated as Mann-Whitney odds, i.e., $WR = MW / (1 - MW)$, where MW is the adjusted Mann-Whitney estimate. This transformation is monotonous in the domain of the Mann-Whitney estimate. The 95% confidence interval for the win ratio will be obtained by transforming the bounds of the confidence interval (

Koch et al 1998) for the Mann-Whitney estimate, using the same transformation as for the win ratio.

Responder analysis:

Number and percentage of patients in each treatment group will be summarized across the following categories:

5 point improvement from baseline to 8 months in TSS vs no significant improvement:

- Change from baseline in $TSS \geq 5$ points, vs
- Death prior to the 8 months assessment or change from baseline in $TSS < 5$ points.

5 point deterioration from baseline to 8 months in TSS vs no significant deterioration:

- Death prior to the 8 months assessment or change from baseline in $TSS \leq -5$ points, vs
- Change from baseline to 8 months in $TSS > -5$ points.

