- In the analysis of rank ANCOVA, the CMH test statistic used for the hypothesis test has a chi-square distribution. In order to apply Rubin’s combination rule, which assumes approximate normal distribution of the statistics being combined, a normalizing Wilson-Hilferty transformation will be applied to the CMH test statistics from each imputed dataset (Ratitch et al 2013). The standardized transformed statistic will be computed as follows:

$$st_{wh_cmh}^{(m)} = \frac{\sqrt[3]{\frac{cmh^{(m)}}{df} - \left(1 - \frac{2}{9 \times df}\right)}}{\sqrt[3]{\frac{2}{9 \times df}}}$$

where $cmh^{(m)}$ is the CMH statistic from the m^{th} imputed dataset and df is the number of degrees of freedom associated with the statistic (in this case equal to 1). The transformed statistics are approximately normally distributed with a mean of 0 and variance of 1 and can be combined using Rubin’s rule.

- For the estimation of the win ratio, a combined Mann-Whitney estimate (MW) and its standard error ($SE(MW)$) will first be obtained by applying Rubin’s rule to the corresponding estimates from multiple imputed datasets. Then the win ratio and its 95% confidence interval will be obtained based on the combined Mann-Whitney estimate and its standard error as previously described.
- For the summaries of number and percentage of subjects in the categories of significant improvement and deterioration from baseline, as discussed in the “Estimation of treatment effect” sub-section above, the average number and percent of subjects in each category across all multiple imputed datasets will be reported. The TSS responder analyses will use the imputation datasets created for the main analysis. Therefore, deaths will be defined as non-responders, and responder status will be determined based on the imputed TSS values for the patients who have missing TSS due to reasons other than death.

Supportive analyses and sensitivity analyses

The number and percent of patients who die prior to the 8-month assessment will be summarized by treatment group.

Descriptive statistics of scores and change from baseline at 4, and 8 months will be presented for total symptom score, overall summary score, clinical summary score and domains (Physical limitation, symptom stability, symptom frequency, symptom burden, quality of life, self-efficacy and social limitation).

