The testing and estimation described for change from baseline at 8 months in TSS, will be repeated in an exploratory fashion for change from baseline in TSS at 4 months, and for the overall summary score and clinical summary scores at 4 and 8 months.

To assess the impact on TSS change from baseline of a treatment effect on mortality, an alternative ranking will be applied, where patients deceased prior to the 8-month assessment will be assigned the same worst rank regardless of their last value while alive. This is done to reduce the impact of treatment differences in time to CV death on the assessment of this KCCQ secondary endpoint.

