Table 4 Distribution of change from baseline KCCQ-TSS at 8 months by change from baseline PGIS at 8 months

	N	(%)	Mean	SD	Min	Q1	Median	Q3	Max	Correlation*
PGIS at 8 Months: 7 Categories										
										0.35
Large Improvement	255	(7)	20.0	22.7	-22.9	2.1	15.6	34.4	90.6	
Moderate Improvement	402	(10)	11.9	18.7	-35.4	0.0	9.4	20.8	72.9	
Small Improvement	831	(21)	9.6	17.4	-49.0	0.0	8.3	17.7	80.2	
Stable	1522	(39)	3.2	15.5	-63.5	-4.2	1.0	10.4	82.3	
Small Deterioration	561	(14)	-3.0	18.2	-71.9	-11.5	-2.1	7.3	50.0	
Moderate Deterioration	223	(6)	-6.9	20.8	-100.0	-17.7	-4.2	6.3	43.7	
Large Deterioration	89	(2)	-11.9	21.6	-65.6	-25.0	-8.3	0.0	54.2	
PGIS at 8 Months: 5 Categories (Version A)										
										0.34
Moderate or Large Improvement	657	(17)	15.0	20.7	-35.4	0.0	10.4	26.0	90.6	
Small Improvement	831	(21)	9.6	17.4	-49.0	0.0	8.3	17.7	80.2	
Stable	1522	(39)	3.2	15.5	-63.5	-4.2	1.0	10.4	82.3	
Small Deterioration	561	(14)	-3.0	18.2	-71.9	-11.5	-2.1	7.3	50.0	
Moderate or Large Deterioration	312	(8)	-8.4	21.1	-100.0	-19.3	-6.3	4.2	54.2	
PGIS at 8 Months: 5 Categories (Version B)										
										0.34
Large Improvement	255	(7)	20.0	22.7	-22.9	2.1	15.6	34.4	90.6	
Small or Moderate Improvement	1233	(32)	10.3	17.9	-49.0	0.0	8.3	19.8	80.2	
Stable	1522	(39)	3.2	15.5	-63.5	-4.2	1.0	10.4	82.3	
Small or Moderate Deterioration	784	(20)	-4.1	19.0	-100.0	-12.5	-2.1	6.8	50.0	

Large Deterioration	89	(2)	-11.9	21.6	-65.6	-25.0	-8.3	0.0	54.2	
---------------------	----	-----	-------	------	-------	-------	------	-----	------	--

^a Absolute value of the Spearman correlation coefficient for change from baseline KCCQ-TSS at 8 months and change from baseline PGIS at 8 months with each categorization
 Categories of change from baseline PGIS at 8 months as defined in Table 3

The eCDF curves in Figure 2 demonstrate a clear separation between all categories of deterioration and the no change category, in the interval between 5 and 20 points decrease in KCCQ-TSS at 8 months. For improvement, the separation is clear between improvement and no change in the interval between 5 and 20 points increase in KCCQ-TSS at 8 months, but the distinction is not as clear between small and moderate improvement. From

Figure 3 it's evident that the combined moderate or large categories of deterioration and improvement are clearly separated from the no change category. This is also observed for combined small or moderate categories of deterioration and improvement in Figure 4.

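### Does the KCCQ win ratio need redefining because its formula splits tied pairs while its definition leaves them out?

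*SAP*

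**What the plan says.** The Win ratio paragraphs of SAP section 4.2.4.2 compare every dapagliflozin patient with every placebo patient and call each pair a win, a loss or a tie. They then state: "Win ratio is defined as the ratio of the number of “winner” pairs to the number of “loser” pairs for the dapagliflozin arm". Ties enter neither term.

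The calculation comes next: "The win ratio statistic will be calculated as Mann-Whitney odds", using the Mann-Whitney estimate adjusted for the randomization stratum and baseline TSS. The confidence limits for MW go through the same transformation. Under multiple imputation the order is kept: MW and its standard error are pooled first, and the "win ratio and its 95% confidence interval will be obtained based on the combined Mann-Whitney estimate" and its standard error.

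The SAP does not say in so many words how a tie enters MW. Two statements in the same section point to an answer. The ranks for the test are formed "using fractional ranks and mean method for ties", and the win ratio is introduced as a summary that "uses the same ranking as that used in the hypothesis test".

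The section also says that the win ratio is not the test statistic, that the two need not agree exactly, and that the claim of superiority comes from the hypothesis test alone.

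**The concern.** With mean ranks, a tied pair contributes one half to MW. MW/(1 - MW) is then (wins + half the ties)/(losses + half the ties), usually called the win odds. That is not wins over losses, unless there are no ties or wins equal losses. Definition and formula thus describe two quantities under one name.

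Ties will occur, because TSS takes a limited set of values. The supportive ranking, in which the deceased "will be assigned the same worst rank regardless of their last value while alive", adds ties by construction.

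The win ratio is the reported effect measure for the third secondary endpoint, chosen for its clinical interpretation. A reader who counts pairs as the definition says would not reproduce the reported figure. If the gap were large, the published effect would be misdescribed.

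**Working it through.** The SAP states no win ratio and no tie rate, so there is no figure of its own to reproduce. The check needs an algebraic relation, a tie rate and a yardstick.

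**Relation.** Let WR be wins over losses and t the share of tied pairs. The win share is (1 - t)WR/(1 + WR) and the loss share is (1 - t)/(1 + WR). Adding t/2 to each and dividing gives

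win odds = [2WR - t(WR - 1)] / [2 + t(WR - 1)].

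This equals WR only if t = 0 or WR = 1; otherwise it lies nearer to 1. It is above 1 exactly when WR is above 1, so the direction of effect and the null value are the same for both.

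**Tie rate.** The source is Appendix B, Table 4 ("Distribution of change from baseline KCCQ-TSS at 8 months by change from baseline PGIS at 8 months"): blinded complete cases, both arms together, seven categories.

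- The category sizes sum to N = 255 + 402 + 831 + 1522 + 561 + 223 + 89 = 3883. The weighted mean is 4.75 and the overall SD is 19.0.
- All 35 minima, quartiles and maxima in the seven-category block are multiples of 100/96 = 1.04 points within rounding. In the collapsed categories two quartiles (-19.3 and 6.8) fall halfway between grid points, as happens when a quartile averages two neighbouring values.
- With similar arms, the tie rate is the sum of squared probabilities over the grid. A hand check with one normal distribution gives grid step/(2 x SD x √π) = 1.042/(2 x 19.0 x 1.772) = 0.0155.
- A mixture of normals with each category's own mean and SD gives 0.0158.
- The smallest tie rate that any distribution on this grid can have while reproducing the seven categories' order statistics, means and SDs is about 0.015.
- Three of the seven categories have a quartile of exactly 0.0, so some excess at zero change is plausible. Assuming an extra 10% of patients at zero (12% in all), the mixture gives 0.0268. Holding 12% at zero and matching Table 4 gives at least 0.0253. The 10% is an assumption.

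**Effect on the estimate.**

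| Wins/losses | t = 0.0158 | t = 0.0268 | t = 0.05 (stress) |
|---|---|---|---|
| 1.20 | 1.1965 | 1.1941 | 1.1891 |
| 1.30 | 1.2946 | 1.2908 | 1.2829 |

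For example, at 1.20 and 0.0158: (2.4 - 0.00316)/(2 + 0.00316) = 1.1965. At the floor of 0.0151 the result is 1.1967.

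**Yardstick.** Take 2250 per arm (4500 randomized 1:1) and no adjustment. SE(MW) = √[(2n + 1)/(12n²)] = √[4501/(12 x 2250²)] = 0.0086. A ratio of 1.20 is MW = 0.5455, with limits 0.5286 and 0.5623, so the interval for the ratio is 1.121 to 1.285 and its half-width 0.082. The shift of 0.0033 to 0.0059 is 4.0% to 7.2% of that half-width.

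**Deaths.** In the main ranking the dead are ordered by their last change in TSS and rank below all survivors, which dilutes the ties. With an assumed 5% dead, 0.0158 becomes 0.95² x 0.0158 = 0.0143, plus the few ties among the dead. In the supportive ranking, tying all the dead adds 0.05² = 0.0025, for a total of 0.0168. A ratio of 1.20 then becomes 1.1963, still within the range above.

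**The case for a change.** The strongest case for a change is that a pre-specified effect measure should be the quantity its definition describes, however small the gap. Nothing in the section drops ties, calls them negligible or names the result win odds. The warning that win ratio and test may disagree does not cover a disagreement between definition and formula. Correcting the wording would cost one sentence and a table label.

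All of this is accurate, and as a matter of naming it stands. Three things limit it.

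- The operational instruction is unambiguous. The formula, the transformation of the limits and the pooling are stated, and the result is called Mann-Whitney odds in the sentence that sets the calculation. Two analysts following the text would produce the same number.
- The sentence on winning and losing pairs explains a raw pair count. The reported statistic is stratified and covariate-adjusted, so it would not in general equal that raw count even with no ties. The SAP defines no adjusted wins-over-losses ratio to set against it.
- Correcting the name would leave the estimator, the interval and the test as they are. Switching to wins over losses would need a new adjusted estimator and interval, to move a descriptive figure by a few thousandths.

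In the other direction, one could object that the one-half rule for ties is only inferred. That is fair, since the tie rule is written for the ranks used in the test, but the shared ranking makes it the natural reading.

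**Conclusion.** The definition and the formula do differ when pairs are tied, and pairs will be tied. It is a slip of labelling and calls for no change to the plan. At tie rates of about 1.5% to 2.7%, a wins-over-losses ratio of 1.20 is reported as 1.197 to 1.194 and one of 1.30 as 1.295 to 1.291. At two decimals that is at most one unit. The shift is toward 1, so it cannot flatter the treatment. The CMH test, the testing hierarchy and the type I error are untouched.

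This rests on ties counting one half in MW, on tie rates approximated from blinded complete-case summaries with the arms taken as similar, and, for the upper rate, on an assumed extra 10% of patients at zero change. The arithmetic is for unadjusted pair shares; the adjusted estimate is assumed to behave on the same scale. Even at 5% tied pairs, 1.20 would be reported as 1.189.
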